## **2.2. Rationale**

Because of the progressive nature of congenital CMV-associated hearing loss, there is a large unmet medical need for treatment options beyond the neonatal period. Data from other CASG investigations support the study of antiviral treatment in infants and toddlers with CMV-associated hearing loss:

- Less than half of the hearing loss due to congenital CMV infection is present at birth.

- Children with congenital CMV continue to excrete virus in the urine for three to five years or even longer.
- The quantity of CMV (viral load) found in the urine and blood is greater in those children destined to develop hearing loss.
- CMV DNA has been detected in the perilymph of children up to four years of age undergoing cochlear implantation for CMV-induced hearing loss.
- Six weeks of IV ganciclovir at 6mg/kg bid given to neonates with congenital CMV disease beginning when they are less than 31 days of age reduces the future incidence of hearing loss.
- Six weeks of intravenous ganciclovir given to neonates with congenital CMV disease beginning when they are less than 31 days of age suppresses viruria, as detected by cell culture, but viruria returns promptly when the drug is stopped, even at the higher dose of 6mg/kg bid.
- The dose of oral valganciclovir that provides the same systemic exposure as the IV ganciclovir dose used in treatment of congenital CMV has been identified, with 16 mg/kg/dose of oral valganciclovir equaling 6 mg/kg/dose of IV ganciclovir.

We hypothesize that six weeks of antiviral therapy can stabilize hearing deterioration in older infants, toddlers, and young children who have developed CMV-associated hearing loss. We will conduct a Phase II study of valganciclovir to test this possibility. We have powered this study to detect a similar difference in audiologic outcomes to that seen when ganciclovir was given for the same duration to neonates and young infants (i.e. worsening of hearing in 41% versus 0% was observed, whereas the more conservative difference of 40% versus 5% has been used for the power calculation for the current study). Since the natural histories of CMV viruria and viremia have not been defined in older children, we anticipate generating valuable data on viral load as a potential biomarker in this population, even if the clinical primary endpoint of hearing is not met. It is possible to envisage utilizing such biomarker data in the development of a future study evaluating a longer duration of valganciclovir or with safer medications.

In the recently completed CASG 112 study of neonates and young infants with symptomatic congenital CMV disease, whole blood viral loads decreased from approximately 3.5 logs to under 2 logs in both groups over the course of the first six weeks of open-label valganciclovir therapy. Viral loads in the two groups of subjects then diverged initially following randomization, but by four months the group randomized to placebo had regained virologic control. By six months the two groups each had approximately 1.5 logs of virus detectable in blood, with the group that had received active drug throughout the six months then experiencing a rebound in viral load as treatment was stopped. Viral load was not assessed beyond month seven. Lower whole blood viral load area-under-the-curve during the first six weeks of therapy was associated with better hearing outcomes at 12 and 24 months in unadjusted ( $p=0.005$  and  $p=0.003$ , respectively) and adjusted ( $p=0.044$  and  $p=0.023$ , respectively) analyses. However, lower whole blood viral load area-under-the-curve from week six to month six was not associated with hearing outcomes in adjusted analyses ( $p>0.168$ ). This suggests that lowering systemic viral load initially aids in improving audiologic outcomes, but that the additional benefit of longer-term treatment for six months may relate to antiviral effects within the inner ear itself, where ongoing viral replication and damage may be impaired with prolonged antiviral therapy. We were not

able to identify specific breakpoints above which the viral load could be used as a biomarker for those patients at higher risk of developmental or hearing sequelae.

Furthermore, we will link this proposed study to the recently introduced national screening programs for hearing loss to demonstrate how CMV screening could be integrated into current diagnostic algorithms employed in the United States and United Kingdom, which offer a potentially cost-effective way to address the unmet medical problem of CMV.

## **2.3. Potential Risks and Benefits**

### **2.3.1. Potential Risks**

The potential risks associated with oral valganciclovir administration relate primarily to the known toxicity of this antiviral agent, neutropenia. Stopping rules are incorporated into this Phase II trial in order to limit exposure of study subjects should the potential risks be unacceptably high.

In addition to neutropenia, the clinical toxicities of valganciclovir include anemia and thrombocytopenia. In animal studies, ganciclovir was carcinogenic, teratogenic, and caused aspermatogenesis. Some additional adverse events reported with valganciclovir are diarrhea, nausea, vomiting and abdominal pain. General disorders reported are pyrexia and fatigue. The most common neurological adverse events reported are headache and insomnia.

The risk associated with blood draws may be discomfort from the needle stick and occasional bruising at the site during or after the blood drawing and rarely an infection. A small clot may form at the site where the needle enters the body.

### **2.3.2. Known Potential Benefits**

Six weeks of intravenous ganciclovir has been proven to protect against hearing deterioration in patients with congenital CMV infection when treatment was initiated during the first month of life. As described above, treatment with oral valganciclovir has the potential benefit of improving hearing outcomes in children with congenital CMV infection and hearing loss who are 1 month through 3 years of age.

## **3. OBJECTIVES**

### **3.1. Study Objectives**

Primary:

- The primary objective is to assess whether a six week course of oral valganciclovir can stabilize the hearing of children with congenital CMV infection who present with hearing loss. This will be accomplished by evaluating changes in hearing in either ear at 6 months from baseline.

Secondary:

- To define the following responses as a function of systemic exposure to ganciclovir (active metabolite of valganciclovir):
  - CMV viral load in blood
  - CMV viral load in urine
  - CMV viral load in saliva
- To define the safety and tolerability of valganciclovir in enrolled subjects.

Tertiary:

- To define the pharmacokinetics of ganciclovir (metabolite) following administration of valganciclovir (prodrug) in enrolled subjects.

### **3.2. Study Outcome Measures**

#### **3.2.1. Primary Outcome Measure**

- Change in total ear hearing assessments (improved + no change versus other) between Baseline and Study Month 6

#### **3.2.2. Secondary Outcome Measures**

- Change in best ear hearing assessments [improved + no change (normal to normal) versus other; improved versus other; worse + no change (abnormal to abnormal) versus other; and worse versus other] between Baseline and Study Month 6
- Change in total ear hearing assessments (improved versus other; worse + no change (abnormal to abnormal) versus other; and worse versus other) between Baseline and Study Month 6
- Detection of viruria by PCR six weeks and six months after trial entry

- The quantitative log reduction in viruria detected after 6 weeks of therapy
- Detection of viremia by PCR six weeks and six months after trial entry
- The quantitative log reduction in viremia detected after 6 weeks of therapy
- Detection of CMV in saliva by PCR six weeks and six months after trial entry
- The quantitative log reduction in CMV viral load in saliva detected after 6 weeks of therapy
- Correlation of change in viral load with change in total ear and best ear hearing at 6 months
- Incidence of unanticipated medically attended visits occurring from Study Day 1 through two weeks following the last dose of study drug
- Incidence of adverse events which lead to permanent discontinuation of valganciclovir therapy or have an unresolved outcome

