### **11.2. Sample Size Considerations**

Subjects will be randomized 1:1 to valganciclovir oral solution or valganciclovir placebo. A **sample size of 54 (27 in each arm)** has 90% power to detect a worsening of hearing from 40% to 8.0% in the treatment group based on analyzing two correlated binary outcomes with correlation coefficient of 0.55 at 2.5% level of significance (using PASS 2008 program). Randomization will be stratified by age at randomization (1 through 11 months, 12 through 23 months, 24 through 35 months, and  $\geq 36$  months) and by CMV involvement (symptomatic and asymptomatic at birth) as a marker of disease severity.

Efficacy and safety analysis will be based on intent-to-treat population (ITT), defined as any child who receives at least one dose of study medication and who has complete hearing assessment data at baseline and Month 6. Children who completed the full six weeks of study medication and have hearing assessment data at baseline and Month 6 will be included in a per protocol (PP) analysis of efficacy, which will be performed as a sensitivity analysis. Since the primary endpoint requires comparison of baseline and 6 month audiology assessments, dropouts and subjects with audiology assessments that are inadequate for study comparison will be replaced.

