## **11.4. Final Analysis Plan**

### **11.4.1. Primary Outcome**

Primary analysis will be based on intent-to-treat population. Categories utilized for hearing assessment of each ear for each time point are normal hearing, mild hearing loss, moderate hearing loss, and severe hearing loss. Based on the hearing assessment of each ear at Month 6 and at Baseline, change in each ear will be categorized into binary outcomes: improved + no change versus other (i.e., worsened). For example, normal in the left ear at baseline and moderate in the same ear at Month 6 will be considered as worsened. The primary outcome will be analyzed using logistic regression based on generalized estimating equations (GEE) in order to accommodate the correlation between the left and right ears of a subject in the modeling. In addition, if there are enough data available we will adjust the analyses by whether or not a subject at birth is asymptomatic or symptomatic from their congenital CMV infection. Additional analyses will be performed to adjust for age and site plus any imbalances in the demographic and clinical characteristics to determine if adding them to the model will impact the results. P-values < 0.05 will be considered significant for the primary outcomes.

A single, independent study audiologist who is masked (blinded) to treatment assignment will assess the audiology test battery for each subject and assign the classifications of normal hearing, mild hearing loss, moderate hearing loss, or severe hearing loss based upon their hearing thresholds (in decibels). The classifications will be assigned by ear (one for the left ear and one for the right ear), giving “total ear” classifications. Following this, the study audiologist will assign the “best ear” classification for the subject at that study visit; for example, if a subject had mild hearing loss in their left ear and severe hearing loss in their right ear, then the “best ear” classification will be mild hearing loss.

Primary analyses will be done on the first 54 subjects recruited. If there were subjects enrolled as replacement for dropouts or missing outcome, these added subjects will be included in the secondary analyses.

For those with missing outcome due to missing baseline and/or Month 6 audiology (including dropouts), we will exclude them from the primary analysis. However, we will perform sensitivity analysis by replacing all missing data with “worsening” outcome.”

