3.3 Derived variables

The primary efficacy assessment will be change in total ear hearing assessment between baseline and 6 months post enrollment. Categories used for hearing assessment of each ear for each time point will be normal hearing, mild hearing loss, moderate hearing loss, and severe hearing loss. Baseline and 6 month hearing categories will be compared and the change in each ear will be categorized into binary outcomes: Improved or no change versus Other (i.e., worsened) Note that the total ear assessment at each time point will be provided by the Independent Audiologist and entered in the database following the rules below and the information provided by the audiology reports.

In the model-based analyses, the “no change” category will be broken down into “Protected: normal to normal” as one category and “No Change: same degree of hearing loss at Baseline and Study Month 6” as another category. The rationale behind this is that if one is interested in the improvement of hearing loss, a subject that has normal hearing at baseline cannot improve further. Hence from an efficacy analysis point of view, the “Protected: normal to normal” can be viewed as protective effect of the drug from hearing deterioration. This analysis approach will be similar to the analysis of the previous CASG study that established the efficacy of 6 weeks of IV GCV in symptomatic congenital CMV disease with CNS involvement.

Analysis of actual viral load will be done using log base 10 transformation. Undetectable viral load value will be replaced by a value of 10. A summary measure of the viral load over time will be calculated two ways. The first approach considers all time points available by calculating the average area under the curve (AUC) (trapezoidal rule) applied to the log base 10 viral load. Average is based on the maximum period of time with viral load data for a given subject. To illustrate, if the calculated AUC for log₁₀ VL for a given subject is 200 from baseline to Day 70, then average AUC is $200/70=2.86$. Taking average AUC will enable us to use and compare data from subjects who did not have viral load values at the later time due to dropping out early, for example, with subjects with complete viral load data. The second approach is to take using difference between Month 6 and baseline log₁₀ VL. The last visit with available VL will be used for those without Month 6 VL. Section 11 contains more details on Viral Load analyses.

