4.3 Inclusion–Exclusion Criteria and General Study Population

(ICH E3;9.3. ICH E9;2.2.1)

Male and female infants from 1 month through 3 years of age (up to 4th birthday) with sensorineural hearing loss will be eligible for enrollment. Following confirmation of inclusion/exclusion criteria and the signing of informed consent, the subject's Guthrie card will be retrieved and tested for CMV DNA by PCR unless there is a virologically confirmed diagnosis of congenital CMV infection made within the first 30 days of life. Inclusion criteria were selected to ensure the inclusion of those subjects with congenital CMV disease. Exclusion criteria were selected to limit confounders for safety and efficacy. Renal insufficiency was an exclusion criterion because the active moiety, GCV, is renally cleared and a neonate's renal system is not fully developed. The study population is consistent with those patients seen in clinical practice and who receive IV GCV as standard of care to treat symptomatic congenital CMV.

Inclusion Criteria

- Signed informed consent from parent(s) or legal guardian(s)
- Sensorineural hearing loss (≥ 21 dB in one or both ears, documented within 12 weeks prior to study entry)
- Children from 1 month through 3 years of age (up to the 4th birthday)
-

Exclusion Criteria

- Imminent demise
- Profound sensorineural hearing loss (> 90 dB) in both ears
- Patients receiving other antiviral agents or immune globulin
- Gastrointestinal abnormality which might preclude absorption of an oral medication (e.g., a history of necrotizing enterocolitis)
- Documented renal insufficiency, as noted by a creatinine clearance < 10 mL/min/1.73m² at time of study enrollment
- Breastfeeding from mother who is receiving ganciclovir, valganciclovir, foscarnet, cidofovir, or maribavir
- Infants known to be born to women who are HIV positive (but HIV testing is not required for study entry).
- Current receipt of other investigational drugs
- Previous receipt of ganciclovir or valganciclovir

- Known hypersensitivity to ganciclovir, valganciclovir, or components of the product
- Inability to attend follow-up hearing and clinical assessments
- Infants with Auditory neuropathy/dyssynchrony.
- Children with another known etiology for SNHL (e.g. connexin 26, syndrome or metabolic disorder associated with SNHL, inner ear malformation and widened vestibular aqueducts, meningitis). Exclusion of each of these conditions is not required for trial enrollment.

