8.2 Secondary Efficacy Analyses

Logistic analyses will be utilized to determine if there is treatment effect based on the best ear outcome. As in the total ear analysis, change in the best ear will be categorized into binary outcomes – namely: improved + no change versus worse; improved + no change (normal to normal) versus worse + no change (abnormal to

abnormal); and improved versus other between baseline and Study Month 6. In addition to the primary outcome, we will analyze the binary outcome for change in the total ears categorized as: improved+ no change (normal to normal) versus worse and improved vs other.

For other secondary and tertiary outcomes, Fisher's exact test will be used to compare binary outcomes (such as detection of viruria or subject with at least one AE or SAE), and Wilcoxon Rank test will be used to compare continuous outcomes (such as quantitative log reduction) between the two treatment groups 6 weeks and 6 months after initial treatment.

Logistic model utilizing generalized estimating equations will also be used to determine the association between change in hearing and change in viral load. Change in viral load over time will be measured by the area under the curve computed using the trapezoidal rule. Spearman rank correlation will be utilized to examine the association between viral load and PK parameters. Poisson regression model will be used to compare the number of AEs/SAEs experienced by subjects between the two groups.

As in the primary outcomes, missing change in hearing outcomes will be replaced by worsened outcomes as sensitivity analyses for all secondary hearing outcomes.

The summary statistics will be produced in accordance with section 7.

9 Safety Analyses

Analyses of safety data will be based on data from all subjects receiving at least one dose of study drug. As per protocol, safety data will be collected only through Study Day 70, i.e., four weeks after the last study dose.

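### The secondary improved-versus-other contrasts count ears that are normal at baseline as non-improvers, which dilutes the improvement rates they report

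*Protocol*

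**What the plan says.** Protocol 3.2.2 sets the total-ear secondary measure as "Change in total ear hearing assessments (improved versus other; worse + no change (abnormal to abnormal) versus other; and worse versus other". The bullet above it gives best ear an improved-versus-other contrast as well. Protocol 11.4.2 and SAP 3.2 repeat both, and SAP 8.2 keeps both; for best ear it reads "and improved versus other between baseline and Study Month 6". None of these places limits the contrast to ears that are abnormal at baseline.

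Three other provisions matter here:

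- **Eligibility** (SAP 4.3; the same in Protocol 5.2): "Sensorineural hearing loss (≥ 21 dB in one or both ears, documented within 12 weeks prior to study entry". A child with one normal ear can therefore enter.
- **Scale** (Protocol 11.4.1): each ear is normal, mild, moderate or severe, and best ear takes the category of the better ear. A child with unilateral loss and a normal other ear starts with a normal best ear.
- **Derived variables** (SAP 3.3): "a subject that has normal hearing at baseline cannot improve further". The SAP uses this to split the no-change class and to treat normal-to-normal as protection.

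The contrasts are tested formally. By their titles, SAP Tables 21d and 22d give modelled treatment effects for each outcome, with p-values. SAP 6.7 plans no multiplicity adjustment for secondary outcomes.

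**The concern.** SAP 3.3 sees the ceiling but repairs only the composite that groups normal-to-normal with improved. In the stand-alone improved-versus-other contrast, a normal ear that stays normal falls into the same class as an ear that worsened. The reported rate then mixes two things: how often impaired ears improved, and how many ears had nothing to improve. The second depends on case mix, not on valganciclovir.

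At stake are the readability of the improvement rates, the size of the reported difference, and some power on a secondary question. Randomization is stratified by age and by symptom status at birth, not by laterality, so chance differences in unilateral loss between small arms add noise to the comparison.

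**Working it through.** **The plan's own figure.** Protocol 11.2 states a "sample size of 54 (27 in each arm" arms layout with "90% power to detect a worsening of hearing from 40% to 8.0% in the treatment group" and a "correlation coefficient of 0.55 at 2.5% level of significance". Sidedness is not given; Protocol 11.4.1 says "P-values < 0.05 will be considered significant for the primary outcomes", which matches a one-sided 2.5% level. With pooled variance:

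- Ears per arm if independent: [1.96·√(2·0.24·0.76) + 1.2816·√(0.40·0.60 + 0.08·0.92)]² / 0.32² = 35.3, rounded up to 36.
- Design effect for two ears: 1 + 0.55 = 1.55. Children per arm: 36 × 1.55 / 2 = 27.9.
- Power at 27 per arm: 89.6%.

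The stated figure is reproduced to within two children in total. It concerns worsening and does not depend on the improved-versus-other contrast.

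**Inputs for this point.** The table in Protocol 2.1 gives unilateral loss in 28/85 symptomatic and 25/48 asymptomatic children with hearing loss. Applying these shares to this trial is an assumption.

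**Share with no possible event.** Let u be the unilateral share, with the other ear normal.

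- Best ear (u): 28/85 = 33%; 25/48 = 52%; pooled 53/133 = 40%. Of 27 children per arm, that is about 9 to 14.
- Total ears (u/2): 28/170 = 16%; 25/96 = 26%.

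**Effect on the estimates.** Reported best-ear rate = (1 − u) × rate among children whose best ear is impaired.

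- Ceiling on the rate, and multiplier on any risk difference: 1 − 0.33 = 0.67 down to 1 − 0.52 = 0.48.
- Example with assumed rates of 40% versus 10% and u = 40%: 0.60 × 40% = 24% and 0.60 × 10% = 6%.
- Risk difference: 30 points becomes 18.
- Odds ratio: (0.40/0.60)/(0.10/0.90) = 6.0 becomes (0.24/0.76)/(0.06/0.94) = 4.9.
- Risk ratio: 4.0 in both.

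**Chance imbalance.** The SD of the between-arm difference in the unilateral share is √(2u(1 − u)/27), which is 12.8 points at u = 33% and 13.6 points at u = 52%.

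**Power for best ear.** The documents plan no improvement rates, so the rates below are assumed (two-sided 5%, normal approximation). Children at risk per arm: 27 × 0.67 ≈ 18, or 27 × 0.48 ≈ 13.

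| Rates among at-risk children | u = 33%: all 27 → at-risk 18 | u = 52%: all 27 → at-risk 13 | If all 27 were at risk |
|---|---|---|---|
| 21% vs 60% | 58% → 68% | 41% → 53% | 85% |
| 21% vs 50% | 39% → 44% | 27% → 33% | 61% |
| 10% vs 50% | 70% → 77% | 52% → 62% | 92% |
| 48% vs 80% | 35% → 52% | 23% → 39% | 70% |

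Restriction gains roughly 5 to 17 points. In most of these rows the larger loss comes from having few children at risk.

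**The case against.** **Improvement is not the trial's main question.** The objective and hypothesis are about stabilizing hearing, and the primary endpoint groups improved with no change. This stands, and it limits the importance of the point.

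**The SAP already handles the ceiling, and an all-children denominator is legitimate.** The composite does answer it for its own contrast, and the share of all treated children who improve is a valid descriptive quantity. Tables 21b, 21c, 22b and 22c and the hearing listing would also let a reader recover much of the at-risk picture. The formally modelled improved-versus-other result stays diluted all the same.

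**The risk difference is not the planned measure.** The analysis is logistic, and the odds ratio in the example moves only from 6.0 to 4.9. This stands; the shrinkage on the planned scale is moderate.

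**Imbalance is ordinary sampling error.** Correct. A reader might infer that a chance imbalance in laterality makes the test invalid, or that the trial cannot address improvement at all. The documents support neither: under randomization the effect is dilution and noise, not bias under the null. Symptom status, along which the 33% and 52% differ, is a stratification factor. That helps only partly, because the SD is still about 13 points at either stratum's share. Adjustment for imbalances is planned, but it is described for the primary outcome.

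**The scale has a mirror limit.** A severe ear cannot move to a worse category, yet it stays in the worse-versus-other contrast. That is a fair observation, but a separate one that does not cure this defect.

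**Conclusion.** The defect is real and confined to secondary endpoints. The improved-versus-other contrasts for best ear and total ears keep ears in the denominator that SAP 3.3 says cannot improve. The primary endpoint and N = 54 are untouched.

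The size rests on an assumption. A reader might take 33–52% as the known share of this trial's children who are fixed as non-improvers. The documents do not support that: the figure comes from a natural-history cohort whose hearing loss accrues to 7–15 years of age, and no expected unilateral share is given for this trial. Excluding bilateral profound loss would raise the share. If 10–30% of bilateral cases were excluded (assumed), it becomes 28/(28 + 57 × 0.9) = 35% to 28/(28 + 57 × 0.7) = 41% for symptomatic children, and 25/(25 + 23 × 0.9) = 55% to 25/(25 + 23 × 0.7) = 61% for asymptomatic children. The younger age range could move it either way.

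Nor does 33–52% apply to the total-ear measure, where the corresponding range is 16–26% of ears. The change is worth making because it is cheap and makes the rate interpretable; the trial's main conclusion does not depend on it.

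**What to change.** In Protocol 3.2.2 and 11.4.2 and in SAP 3.2 and 8.2, define the improved-versus-other contrasts for best ear and total ears among ears classed mild, moderate or severe at baseline. Report normal-at-baseline ears separately, by arm, as protected or worsened. The all-ears version may stay as a descriptive summary.

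The cost is wording and one filter on a category that the masked audiologist already assigns. The baseline hearing window closes on Day −1, before the first dose, so the restriction involves no selection by treatment. No improvement event is lost, because the excluded ears cannot have one.

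The downside is a smaller denominator, about 13 to 18 of 27 children per arm for best ear under the same assumption. The restriction does not restore the power lost to having few children at risk; its main gain is a rate that means what its label says.
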